Consortium:	Developmental Synaptopathies Consortium

Double in other a Oite a	Destan Ohildrania Hasnifal	
Participating Sites:	Boston Children's Hospital	
	Cleveland Clinic	
Activation Date:	Stanford University Medical Center June 9, 2017	
Current Status:		
Sample Size:	Open to Enrollment 40 randomized	
Target Enrollment Period:	2 Years	
	Interventional, Phase I/II, Multi-Center	
Study Design: Primary Study Objective:		
Filliary Study Objective.	To evaluate the safety of everolimus compared with placebo in patients with PTEN mutations	
Secondary Study	To evaluate the efficacy of everolimus on neurocognition and	
Objective(s):	behavior in patients with PTEN mutations compared to placebo as	
Objective(3).	measured by standardized, direct and indirect neurocognitive tools	
	and behavioral measures (processing speed/working memory).	
Study Population and Main	Double-Blind Inclusion Criteria	
Eligibility/ Exclusion		
Criteria:	1. Male and female outpatients between 5 and 45 years of age	
	(inclusive);	
	2. Pathogenic PTEN mutation confirmed by clinical genetic	
	testing;	
	3. Participant must be able to complete one of the following three	
	standardized assessments: Conners' Continuous Performance	
	Tasks (CPT-3-mean reaction time), Stanford Binet (SB-5;	
	working memory), or the Purdue Pegboard Test;	
	4. Performance below the age-adjusted population mean on at	
	least one of the above standardized measure: attention (CPT-	
	3, mean reaction time), working memory (SB5), or fine motor	
	skills (Purdue Pegboard Test; either dominant hand, non-	
	dominant hand, or both hands);	
	5. Adequate bone marrow function as shown by:	
	a. platelets ≥ 80,000/mm³	
	b. absolute neutrophil count ≥ 1,000/mm³	
	c. hemoglobin ≥ 9 g/dL 6. Adequate liver function as shown by:	
	a. Total serum bilirubin < 1.5 x ULN	
	b. AST and ALT levels < 2.5 x ULN	
	c. INR ≤ 2	
	7. Adequate renal function: serum creatinine < 1.5 x ULN,	
	8. Signed informed consent obtained prior to any screening	
	procedures;	
	9. Individuals on psychotropic and anti-epileptic medications	
	should maintain a stable dose for at least 2 months prior to the	
	screening visit;	
	10. Negative serum pregnancy test for females at screening and	
	no plans to become pregnant or conceive a child while	
	participating in the study. The effects of mTOR inhibitors on the	
	developing fetus at the doses used in this study are unknown.	
	For this reason, women of child-bearing potential and men	

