This protocol addresses a key area of interest: Pharmacological treatments of a well-defined subgroup with autism spectrum disorder. It will leverage an existing investigation that aims at examining the natural history study of individuals with autism and germline heterozygous PTEN mutations (BCH IRB-P00013150: Natural History Study of Individuals with Autism and Germline Heterozygous PTEN Mutations). The purpose of this

phase II pilot study will be to establish short-term safety of everolimus treatment in individuals with germline PTEN mutations and evaluate associated cognitive and behavioral changes in this population to generate plausible hypotheses to be tested in a future Phase III confirmatory trial. This protocol also mirrors a previous clinical trial utilizing everolimus in the tuberous sclerosis population (BCH 10-06-0247 Randomized Double-Blind Phase 2 Trial of RAD001 for Neurocognition in Individuals with Tuberous Sclerosis Complex).

In this investigation, we propose a 6-month randomized, double-blind, multi-site study to evaluate the safety and efficacy of a rapamycin analogue, everolimus, to treat neurocognitive and social deficits in a total of 60 patients (age range 5-45 years) with a PTEN mutation with a maximum of 40 participants randomized to treatment. By maintaining a lower age limit of 5 years, we can ensure a more accurate assessment of cognitive and behavioral outcomes, streamline the neurobehavioral assessment battery, and with minimal loss to outcome measure scope and sensitivity, similar to the strategy we employed in a previous everolimus trial in tuberous-sclerosis complex (TSC) (NCT01289912), performed by PI [name]., Ph.D.

This investigation involves 3 participating sites (Stanford University, site PI: [name].; Cleveland Clinic, site PI: [name].; and Boston Children's Hospital, site PI: [name]., Ph.D.).

2. Objectives and Endpoints

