4.1 Study Rationale

This is a phase II, double-blind, randomized, parallel group, placebo-controlled, three center study evaluating treatment with everolimus versus placebo in 40 patients with PTEN gene mutations, ages 5-45 years (inclusive). It is expected that 60 patients will need to be screened to have 40 who will meet inclusion and exclusion criteria.

There are four different phases in this study: pre-treatment (screening), a 6-month blinded treatment phase, a 6-month open label phase for patients initially randomized to placebo, and a follow-up phase. Each of these phases is described in detail below.

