17.1 Power Estimation

This is the first study to evaluate the efficacy of everolimus in patients with a PTEN mutation and ASD/DD. As such, analyses will be predominantly descriptive with the intent of generating plausible hypotheses to be tested in a Phase III confirmatory trial. The planned recruitment sample size of 40 was based on three considerations: 1) the expected recruitment potential of the three sites, 2) a desire to ensure sensitivity to any enrichment in side effects or problems with tolerability in everolimus treated patients, and 3) the need for adequate statistical power in examining primary and secondary efficacy outcomes. Assuming an overall dropout rate of approximately 10%, 44 patients will need to be enrolled to get 40 patients with complete trial data. However, following intent to treat procedures, all patients who are randomized, dosed, and for whom baseline data is collected will be included in statistical analyses. Statistical power considerations for each aim/hypothesis are described below. Except for safety analyses, where only everolimus-treated patients would be expected to show enrichment of dropout or side effects, statistical power estimates are based on one-tailed significance tests with Type 1 error rate of α =.05.

Primary Objective- Safety. The planned sample size of 40 is underpowered to detect small differences in dropout rates or side effects between everolimus versus placebo-treated groups. Statistical power will only be adequate if at least a 35% difference in the proportion of dropout/side effects is observed (1- β ≥.81), assuming a one-tailed Type 1 error rate of α =.05. This is equivalent to 1/20 patients experiencing an adverse event/side effect in the placebo arm and 8/20 in the treated arm. Similarly, statistical power of survival analyses will only be fair (1- β ≥.57) if a hazard ratio of 7.5 is observed, equivalent to a 5% dropout rate in the placebo group versus a 30% dropout rate in the everolimus group. However, because the goal is to maintain sensitivity to any potential enrichment in dropout or side effects, any indicator showing a difference of 10% or greater will be considered a meaningful difference and will be reported.

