Secondary Objective – Efficacy. For power estimation purposes, the variability in PTEN patients treated with an mTOR inhibitor is expected to be similar to the untreated sample. Preliminary data indicates that the measures which comprise the dominant portion of the neurocognitive composite index (processing speed working memory, and fine motor) are highly sensitive to the brain dysfunction seen in PTEN patients with ASD. The effect sizes are approximately 1 SD or larger. In a comparison between mTOR treated vs. untreated PTEN patients, an effect size of at least 0.65 SD would be of interest and represent clinically- meaningful improvement. For example, an effect size of at least 0.65 SD on cognitive measures would translate to a 10-point standard score improvement in the everolimus-treated group relative to placebo. An improvement of 10 or more points is outside the standard error of measurement for most cognitive measures and is typically considered a reliable change when disordered populations are re-tested.

A sample size of 40 (20 per arm) patients will permit detection of endpoint (6-month follow-up) differences of at least 0.80 SD at the 5% significance level (one-sided alpha = 0.05) with 80% power (1- β). Statistical power will be weaker (1- β =.65) if smaller cross-sectional differences are observed (0.65 SD). However, statistical power is very strong, even for smaller differences (Cohen's d≥.50 equivalent to ≥.50 SD difference) when the full repeated measures nature of the design is considered – baseline, 3-month follow-up, 6-month follow-up. Assuming even modest correlations between repeated measurements of outcome variables (r≥.30), power to detect clinically meaningful differences of .50 SD is very good (1- β =.83; one-sided α =.05). If the primary outcome measure (neurocognitive composite) meets nominal statistical significance in the expected direction (one-tailed p<.05) or a secondary outcome measure meets a more stringent false discovery rate-corrected

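### Section 17.1 asks for 44 enrolled to yield 40 complete, but randomisation is capped at 40; the stated 80% and 65% endpoint power carry no drop-out allowance

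*Combined protocol and SAP*

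**What the plan says.** Section 17.1 opens its justification with 40: "The planned recruitment sample size of 40 was based on three considerations". Two sentences later it allows for about 10% drop-out and concludes that "44 patients will need to be enrolled to get 40 patients with complete trial data". It then adds that, under intention to treat, all patients randomised and dosed with baseline data will be analysed.

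The other sections leave no room for 44. The synopsis gives 40 randomised as the sample size. Section 1 describes 60 patients "with a maximum of 40 participants randomized to treatment". Section 4.1 says: "It is expected that 60 patients will need to be screened to have 40 who will meet inclusion and exclusion criteria".

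The efficacy power statement in Section 17.1 is built on 40: "A sample size of 40 (20 per arm) patients will permit detection of endpoint (6-month follow-up) differences of at least 0.80 SD", with 80% power at one-sided alpha 0.05. At 0.65 SD the stated power is .65. For the repeated-measures analysis, with correlations of at least .30, the section says that "power to detect clinically meaningful differences of .50 SD is very good" (.83, one-sided .05).

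The efficacy analyses in Section 17 are a mixed model over baseline, Month 3 and Month 6 fitted by maximum likelihood under MAR, a version of it with baseline as a covariate, and an ANCOVA of the endpoint controlling for baseline.

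**The concern.** The 44 in Section 17.1 cannot be squared with a cap of 40. Reading enrolled as screened does not help: the screening figure is 60, and drop-out that leaves complete trial data can only occur after randomisation. If 40 are randomised and the plan's own drop-out applies, the endpoint comparison will not have 20 per arm, yet the quoted power assumes that it will.

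Two things are at stake. Section 17.1 lists adequate power for the efficacy outcomes among its three reasons for the sample size, and it uses significance on the composite to nominate outcomes for Phase III, so the assumed chance of missing a real effect affects how a null result is read. Also, a site or IRB cannot tell from the text whether 40 or 44 patients may be randomised.

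A related inconsistency sits in the same passage. An effect of at least 0.65 SD is called clinically meaningful and tied to a 10-point change; the next paragraph applies the same label to .50 SD, where power is described as very good.

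**Working it through.** **Inputs.** 40 randomised at most (synopsis, Sections 1 and 4.1); 1:1 allocation (Section 4.3); about 10% drop-out, one-sided alpha 0.05, and effects of 0.80 and 0.65 SD (Section 17.1).

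**Expected Month 6 data.** 40 × 0.90 = 36, or 18 per arm.

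**Unadjusted comparison of means.** With n per arm and effect d in SD units, the noncentrality is d × √(n/2) on 2n − 2 degrees of freedom; power comes from the noncentral t distribution.

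| n per arm | d | Noncentrality | Critical t | Power | Stated |
|---|---|---|---|---|---|
| 20 | 0.80 | 2.530 | 1.686 (38 df) | 0.799 | 80% |
| 20 | 0.65 | 2.055 | 1.686 | 0.646 | .65 |
| 18 | 0.80 | 2.400 | 1.691 (34 df) | 0.760 | – |
| 18 | 0.65 | 1.950 | 1.691 | 0.605 | – |

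The first two rows reproduce the plan. A two-sided test does not (0.693 and 0.517). The stated figures are therefore those of an unadjusted one-sided test with all 40 observed at Month 6. At 18 per arm each falls by about 4 points, and the difference detectable with 80% power rises from 0.80 to 0.846 SD.

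**Baseline-adjusted ANCOVA at 18 per arm.** Adjustment divides the residual SD into a larger effective effect, d / √(1 − r²), on 2n − 3 = 33 degrees of freedom (critical t 1.692), where r is the baseline-to-endpoint correlation.

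| r | d | Noncentrality | Power |
|---|---|---|---|
| 0.30 | 0.80 | 2.516 | 0.794 |
| 0.30 | 0.65 | 2.044 | 0.639 |
| 0.50 | 0.80 | 2.771 | 0.857 |
| 0.50 | 0.65 | 2.252 | 0.712 |

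The plan gives .30 as a lower bound for correlations between repeated measurements; using it for baseline to Month 6 is an assumption, and 0.50 shows the range.

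**Maximum-likelihood Month 6 contrast without baseline adjustment.** Assume r = 0.3 throughout, half of the drop-outs seen at Month 3, and a normal approximation. Power is 0.779 and 0.624 with 10% drop-out, against 0.812 and 0.659 with none. Keeping drop-outs in the model recovers only part of the loss.

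**Repeated-measures .83.** The only match found is an F test of the group-by-time interaction with f = d/2 = 0.25, three time points, r = 0.3 and alpha 0.05. The noncentrality is f² × N × 3 / (1 − r). For N = 40 it is 0.0625 × 40 × 3 / 0.7 = 10.71 and power is 0.827. For N = 36 it is 9.64 and power is 0.781. This figure also assumes 20 per arm.

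**Effect-size labels.** On the plan's scale, where 0.65 SD is 10 points, .50 SD is 10 × 0.50 / 0.65 = 7.7 points, below the 10-point change used to justify the label.

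**The case against.** The strongest reply is that an unadjusted comparison of completers at Month 6 is not one of the planned analyses. This stands. A reader might infer from 0.76 and 0.60 that the trial cannot deliver its stated power; the documents do not support that, because the planned ANCOVA at 18 per arm gives practically the stated values at r = 0.30 and exceeds them at r = 0.50. What remains is that Section 17.1 does not base its 80% and 65% on that analysis: they reproduce without adjustment and without drop-out.

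A second reply is that 10% drop-out need not mean 10% without endpoint data. Section 17.1 keeps all randomised and dosed patients with baseline data in the analysis, Section 7.7.6 schedules those who stop drug for an end-of-treatment assessment, and Sections 3.5 and 7.9.3 say that the composite tolerates one or two missing measurements. This has some force, so 36 is an expectation at the cautious end. But the Section 7.7.6 visit is to take place soon after stopping, not at Month 6, and a mixed model retains drop-outs without supplying their Month 6 values.

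A reader might also object that 40 / 0.9 = 44.4 calls for 45 rather than 44. That is rounding on a rate given only as approximate (44 × 0.9 = 39.6) and is not an error worth raising.

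**Conclusion.** The point holds as an internal contradiction and a modest overstatement. The text requires 44 and permits 40, and the two endpoint power figures belong to 20 observed per arm. With about 36 observed, the same unadjusted test has power of about 0.76 at 0.80 SD and 0.60 at 0.65 SD; at 0.65 SD the chance of missing the effect is about 40% rather than 35%. This rests on the plan's 10% drop-out, equal loss in the two arms, and no Month 6 data from drop-outs. Under ANCOVA the shortfall nearly vanishes at r = 0.30 and reverses at 0.50.

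The trial is described as exploratory and efficacy is its secondary objective, so no analysis or decision rule changes. The safety power figure is not eroded in the same way, because drop-out is itself the endpoint there. A reader might infer that 0.65 SD must be the true clinical threshold because it is the one given a rationale; the documents show only that two values carry the same label, not which one the sponsor should hold.

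**What to change.** In Section 17.1, keep 40 randomised and remove the 44-patient sentence, or reconcile it with the synopsis and Sections 1 and 4.1. Then restate every efficacy power figure for 40 randomised and about 36 with Month 6 data, naming the analysis and correlation behind each:

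- Unadjusted endpoint comparison, one-sided 0.05: 0.76 at 0.80 SD, 0.60 at 0.65 SD, and 80% power at about 0.85 SD.
- If the sponsor prefers to rest on ANCOVA: about 0.79 and 0.64, with the assumed baseline-to-endpoint correlation of 0.30 stated.
- Repeated-measures analysis: replace .83 with a figure on the same basis, and state the test used. The F test that reproduces .83 gives about 0.78 at 18 per arm. Leaving .83 alone would mix 36 and 40 patients in one paragraph.

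Reconcile the two uses of clinically meaningful, 0.65 SD and .50 SD, so that the label and the 10-point rationale refer to the same effect.

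The cost is a change of wording and a slightly less favourable stated power. No extra patients and no change in conduct are needed.

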In objective 2, we will examine whether the everolimus group will show more improvement, compared to the placebo group, on the main neurocognitive efficacy composite outcome. Randomization Group (everolimus versus placebo) differences on the neurocognitive composite will be analyzed using mixed effects (growth curve) modeling, fully utilizing repeated measurements collected at three points (Time: baseline, 3-month follow-up, and 6-month follow-up). A significant interaction between Time and Randomization Group, with the everolimus group showing a more favorable outcome trajectory, will support the primary efficacy hypothesis. Maximum likelihood estimation will be implemented in the Mplus program version 7.2 or above.

Mixed effects (growth curve) model analyses will be conducted following the intention-to-treat principle. Data points that are missing due to subject attrition will be handled assuming that data are missing at random (MAR) conditional on observed information, which is less restrictive than missing completely at random (MCAR) assumed in fixed effects analyses such as ANCOVA and regression analysis. In this procedure, all available cases including the ones with missing information will be included in the analyses. By including every subject who completed at least one assessment, we are not only more likely to conserve power, but also less likely to produce biased effect estimates. In mixed effects analyses, the slope of the outcome will be modeled as the key

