dependent variable predicted by randomization group. We will conduct the analysis with and without conditioning on relevant baseline covariates. The results of these longitudinal analyses can be easily converted to a cross-sectional group effect at each assessment time point to describe the magnitude and significance of group differences. Of particular interest is the group difference at end of treatment (6-month assessment). The mixed effects analyses will be repeated using a model where the baseline scores on each outcome are treated as a baseline covariate to control for (instead of as a part of) the repeated measures. This model can be useful if there is a considerable heterogeneity between before and after treatment processes. We will also analyze the data using conventional ANCOVA treating the end point neurocognitive composite as the dependent variable and controlling for the baseline neurocognitive composite. Further analyses will be conducted using the same analysis models but with transformed data (e.g., log transformation) to check the sensitivity of the results to deviation from outcome normality. Statistical significance of all main effects and interaction terms as well as cross-sectional group differences will be determined using a one-tailed Type 1 error rate of α =.05. The same analysis strategy will be employed for secondary efficacy outcomes and a false discovery rate correction will be implemented to control inflation of Type 1 error.

If the exploratory biosample objectives are pursued, we will explore whether baseline peripheral blood levels of PTEN-associated pathway molecules (PI3K/AKT, mTOR, MAPK protein levels) change with treatment and if changes in peripheral pathway molecules correlate with clinical improvement. To determine whether PTEN-associated pathway molecules change with treatment, we will use a similar mixed effect (growth curve) modeling approach to that described above for Secondary Objective with screening, 3-month, and 6-month pathway measurements as outcome measures. The Time by Randomization Group interaction will test whether the everolimus treatment group shows improvement/normalization of PTEN-pathway molecule levels relative to placebo. This component will be dependent on securing additional funds.

In analyzing the resting state EEG and AEP data we will focus on the following:

- 1. Baseline EEG gamma power
- 2. AEP N1 habituation

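### The stated 0.83 power for a 0.50 SD difference at r≥.30 is not what the planned slope test has: about 0.37 at r=.30, reaching 0.83 only near r=.82

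*Combined protocol and SAP*

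**What the plan says.** Section 17.1 (Secondary Objective – Efficacy) first gives cross-sectional Month 6 powers for 20 per arm at one-sided alpha .05: 80% for 0.80 SD and 0.65 for 0.65 SD. It then says that with baseline, Month 3 and Month 6 used together "statistical power is very strong, even for smaller differences", and that at correlations of .30 or above "power to detect clinically meaningful differences of .50 SD is very good (1- β =.83; one-sided α =.05"). Earlier in the same section the threshold of clinical interest is higher: "an effect size of at least 0.65 SD would be of interest".

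The test that this power should describe is in section 17, objective 2. There "the slope of the outcome will be modeled as the key" dependent variable, predicted by randomization group, and "A significant interaction between Time and Randomization Group, with the everolimus group showing a more favorable outcome trajectory, will support the primary efficacy hypothesis". On missing data, "all available cases including the ones with missing information will be included in the analyses". A further analysis is a "conventional ANCOVA treating the end point neurocognitive composite as the dependent variable and controlling for the baseline neurocognitive composite".

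On numbers, section 17.1 assumes about 10% dropout and says "44 patients will need to be enrolled to get 40 patients with complete trial data", while section 1 caps randomization at 40.

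**The concern.** Repeated measures do not automatically add power to a slope test. With a weak correlation between visits, the change from baseline is noisier than a single visit, so the test loses power against a plain Month 6 comparison. A jump from below one half at the endpoint to 0.83, at a correlation of only .30, is therefore implausible for a Time-by-Group test.

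The plan concedes modest endpoint power at 0.65 SD and then offsets it with the 0.83. Nothing else supports that reassurance, and adequate efficacy power is one of three reasons given for n=40. A reader deciding whether a non-significant composite is informative would rely on a figure that is too high. The composite's one-tailed p<.05 is one of two routes to Phase III candidacy; FDR-significant secondary outcomes are the other.

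**Working it through.** **Inputs from sections 17 and 17.1:** n = 20 per arm, common SD (set to 1), one-sided alpha .05, three visits (0, 3, 6 months), difference d = 0.50, r = .30 as the floor.

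**Assumptions not in the documents:** equal baseline means, linear divergence reaching d at Month 6, the same correlation between all pairs of visits, complete data unless stated. The documents give no r for the composite, so a range is shown.

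**Step 1: reproduce the plan's endpoint figures.** For a one-sided two-sample t-test, SE = √(2/20) = 0.316 with 38 df.
- d = 0.80: 0.80/0.316 = 2.53, power 0.799 (stated 0.80).
- d = 0.65: 0.65/0.316 = 2.06, power 0.646 (stated 0.65).
- d = 0.50: 0.50/0.316 = 1.58, power 0.463.

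Both stated values reproduce, so alpha, n and SD are being read as the plan intends.

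**Step 2: the slope test.** With three equally spaced visits and equal correlations, the slope is the Month 6 minus baseline change divided by time; Month 3 has zero weight. The change has variance 2(1−r), so SE = √(2(1−r)·2/20).
- r = .30: SE = √(1.4 × 0.1) = 0.374; 0.50/0.374 = 1.336; power 0.370 (60,000-trial simulation 0.370).
- r = .50: SE = 0.316, the same as the endpoint test; power 0.463.
- r = .70: SE = √(0.6 × 0.1) = 0.245; 0.50/0.245 = 2.04; power 0.641.
- Power 0.83 is reached at r = 0.822.

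| Test, 20 per arm | r=.30 | r=.50 | r=.70 | r=.80 |
|---|---|---|---|---|
| Slope, 0.50 SD at Month 6 | 0.37 | 0.46 | 0.64 | 0.79 |
| Slope, 0.65 SD at Month 6 | 0.52 | 0.65 | 0.83 | 0.94 |
| Month 6 ANCOVA, 0.50 SD | 0.49 | 0.56 | 0.70 | 0.83 |
| Month 6 ANCOVA, 0.65 SD | 0.68 | 0.75 | 0.88 | 0.96 |

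ANCOVA uses SE = √((1−r²)·2/20) with 37 df. At r = .30 the slope test would reach 0.83 only with a Month 6 difference of 0.99 SD, or with 77 per arm at 0.50 SD.

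**Step 3: more favourable readings of 0.50 SD at r = .30.**
- Mean of both post-baseline visits, baseline-adjusted, full effect already present at Month 3: variance (1+r)/2 − r² = 0.56, power 0.67.
- Average of all three visits, full difference present even at baseline: variance (1+2r)/3 = 0.533, power 0.68.

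Neither reaches 0.83.

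**Step 4: where 0.83 may come from.** A generic within-between interaction F test with f = d/2 = 0.25, N = 40, m = 3 has λ = 0.0625 × 40 × 3/0.7 = 10.71 on 2 and 76 df, and power 0.827. But group differences of 0, 0.25 and 0.50 SD give deviations of ±0.125 and 0 about the mean, so f = √((2 × 0.125²)/3) = 0.102. Scaling up, f = 0.25 corresponds to 0.50 × 0.25/0.102, or about 1.22 SD at Month 6. Separately, a slope of 0.50 SD per 3-month interval gives 0.836, but that is 1.0 SD at Month 6.

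**Step 5: 10% dropout.** With 18 per arm complete, 2 per arm lacking Month 6 and all available data used, slope power for 0.50 SD is 0.35, 0.44 and 0.61 at r = .3, .5 and .7. Endpoint t-tests on 18 completers per arm give 0.760 at 0.80 SD and 0.605 at 0.65 SD.

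**The case against.** The strongest objection concerns the model. Section 17 says the slope is predicted by group and does not say outright that the intercept is too. If the groups are constrained to a common baseline, which randomization justifies, power for 0.50 SD is 0.52, 0.57, 0.71 and 0.83 at r = .3, .5, .7 and .8. The statement that the slope test is weaker than the endpoint test at r=.30 then no longer holds. The calculation is right and worth showing. However, section 17 also plans tests of all main effects and interactions and a group difference at each assessment, which points to a free group term at baseline. Under either specification, 0.83 is far off at r=.30.

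Second, sections 3.5 and 7.9.3 expect the composite to be highly reliable. If r is 0.80 to 0.85, slope power for 0.50 SD is 0.79 to 0.88. That is true, but the plan claims 0.83 from modest correlations upward and gives no estimate of r.

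Third, the plan never defines the 0.50 SD effect, so Month 6 is an inference. That stands as a caveat. The text does equate it with Cohen's d, though, and the only slope reading that fits (0.50 SD per interval) doubles it at Month 6.

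Fourth, efficacy is secondary, the analyses are mainly descriptive, and the candidacy rule uses p-values rather than power. This limits the consequence but does not make the figure correct. The 44-versus-40 conflict is a separate matter that does not bear on the 0.83.

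**Conclusion.** The concern holds. At the stated correlation of .30, the planned Time-by-Group test has power of about 0.37 for a 0.50 SD Month 6 difference (0.52 if baseline is constrained equal), not 0.83. With the free baseline term it would miss such a difference about 63% of the time. Even at the plan's 0.65 SD threshold its power at r=.30 is 0.52. These figures rest on equal correlations, linear divergence and 20 complete patients per arm. The conclusion that 0.83 is unsupported at r=.30 does not depend on the choice of model, since the most favourable reading of a 0.50 SD difference reaches about 0.68.

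Two smaller inconsistencies also stand: both 0.65 and 0.50 SD are presented as clinically meaningful, and 44 enrolled cannot be squared with a maximum of 40 randomized. The matter should be fixed, but it does not threaten the design.

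**What to change.** In section 17.1:

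1. Delete the 0.83 and the descriptions of repeated-measures power as very strong and very good.
2. Define the effect as the group difference at Month 6 and keep one clinically meaningful value, 0.65 or 0.50 SD.
3. Give power for the planned one-sided slope test over a range of r labelled as an assumption: 0.37 to 0.64 for 0.50 SD and 0.52 to 0.83 for 0.65 SD at r = .3 to .7, noting that 0.83 at 0.50 SD needs r of about .82. Beside it show the already planned Month 6 ANCOVA: 0.49 to 0.70 and 0.68 to 0.88. State whether the model allows a group difference at baseline; if not, use the constrained figures.
4. Reconcile 44 enrolled with the cap: keep 40, and say that with about 36 completers the endpoint t-test powers are about 0.76 at 0.80 SD and 0.60 at 0.65 SD. Report the slope-model figures under 10% dropout separately (0.35, 0.44 and 0.61 for 0.50 SD at r = .3, .5 and .7).

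The cost is text in the power section, which can go into the next written amendment under section 18, and a less favourable stated power. The main efficacy test, sample size and visits stay as they are.
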